6.1 General Study Design and Plan

(ICH E3; 9)

This is a phase IV, randomised superiority trial that is blinded to the primary outcome assessors, but open label to all other investigators and participants. The control arm is the standard annual dose of praziquantel, intervention arm 1 is a twice yearly dose of praziquantel and intervention arm 2 is a four yearly dose of praziquantel. Randomisation will be 1:1:1 to each arm and stratified by school.

Trial Flow Chart

pathological responses.

Blood sample collection for monitoring of host immuno-

NB! Only 120 participants sampled at 12 months and only parasitology egg counts and only pre-treatment.

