9.1.2 Consort Flow Diagram

9.2 Derived variables

Periportal Fibrosis is a binary outcome:

WHO ultrasonography Niamey protocol pattern scores of C, D, E or F=1 (i.e. has periportal fibrosis)

WHO ultrasonography Niamey protocol pattern scores of A or B=0 (i.e. does not have periportal fibrosis)

Kato-Katz egg counts

o Eggs Per Gram

The epg value for each participant visit is calculated in the macro database as the mean of the kato-katz slide egg counts from a maximum of 3 stool samples multiplied by an adjustment factor (one stool sample is sufficient for protocol adherence at a particular time point).

Helminth distributions within the human host are highly over dispersed therefore the epg values for each participant will be log transformed using natural logs (In).

A constant value of 1 will be added to all raw epg values to allow for the possibility of an epg value of 0.

$$\sum (\ln(epg+1))$$

The geometric mean epg will be calculated as below:

$$e^{\frac{\mathcal{E}(\ln(epg+1))}{n}} - 1$$

95% Cl's calculated on the logarithmic scale can also be converted back to the original scale by exponentiating and subtracting 1.

Egg Reduction Rate (ERR)

Sample Egg Reduction Rate will be estimated as:

$$(1-(epg2 \div epg1) \times 100)$$

Where epg1 and epg2 are the arithmetic mean of epg of faeces at:

- baseline and at 24 months + 4 weeks
- baseline and baseline + 4 weeks
- o 24 months and 24 months +4 weeks

o **Heavy Infection**

The WHO classifies 'Heavy infection' as those with epg counts of \geq 400. Where the percentage of children with of heavy infection is < 5% then morbidity control is considered to have been achieved and if the percentage of heavy infection is < 1% then the disease is considered to have been eliminated as a public health concern.

Heavy Infection: Binary variable $-1 = "yes" = epg \ge 400$, 0 = "no" = epg < 400 or not detectable

Disease status

Disease status is a binary variable where 0 = No disease (epg =0); 1 = Disease (>0 epg)

Point Prevalence (PP)

Is a measure of disease frequency and quantifies the proportion of individuals in a population who have Schistosomaisis mansoni at a specific instant in time.

$$PP = \frac{Total\ number\ of\ participants\ who\ have\ an\ average\ epg > 0}{Total\ number\ of\ participant\ at\ risk}$$

Total number of participants at risk will include all participants for whom at least one stool sample was collected at the timepoint being assessed.

Cure Rate (CR)

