10.2.4 Analysis of secondary endpoint - Egg Reduction Rate

A mixed model repeated measures analysis with an unstructured covariance matrix for the within - patient residual errors will estimate the Egg Reduction Rate (ERR) between:

- o baseline and 24 month +4 weeks
- baseline and baseline + 4 weeks
- o 24 months and 24 months + 4 weeks

for each treatment group using log transformed epg counts at 3 time points (baseline +4 weeks, 24 months and 24 months + 4 weeks). The model will specify fixed effects of treatment, time and baseline epg count with an interaction term between treatment and time. A weight argument will allow a distinct variance for each time point. The treatment effect coefficient (βx) in this model quantifies the relative change and the ERR is given by $1 - \exp(\beta x)$.

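### SAP 10.2.4 equates the model-based egg reduction rate with 1 − exp(treatment coefficient), which is a between-arm ratio at one visit and not a reduction between two visits in any arm

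*SAP*

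**What the plan says.** Section 9.2 defines the sample ERR as one minus the ratio of a later to an earlier mean count, as a percentage: "Where epg1 and epg2 are the arithmetic mean of epg of faeces at" the two ends of each of three intervals. These are baseline to baseline + 4 weeks, baseline to 24 months + 4 weeks, and 24 months to 24 months + 4 weeks. ERR is therefore a change over time within a group.

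Section 10.2.4 says that a repeated-measures model "will estimate the Egg Reduction Rate (ERR) between" the same pairs of visits, for each treatment group. Three arms and three intervals make nine values. The response is built "using log transformed epg counts at 3 time points (baseline +4 weeks, 24 months and 24 months + 4 weeks", so baseline is not a response visit. "The model will specify fixed effects of treatment, time and baseline epg count with an interaction term between treatment and time". The section closes with "The treatment effect coefficient (βx) in this model quantifies the relative change and the ERR is given by" 1 − exp(βx).

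Sections 5.1.3 and 5.2.2 list ERR as exploratory, although the heading of 10.2.4 calls it secondary.

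**The concern.** The quantity promised and the quantity computed differ. An ERR compares one arm with itself at an earlier visit. The treatment coefficient in the stated model compares one arm with another at the same visit. The formula attaches the name of the first to the second.

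A programmer who follows the sentence would produce a value for the 2x and 4x arms only, and each would be a between-arm reduction. A report could then show a high descriptive ERR in one table and a model-based ERR near zero in another, both under the same label and both produced as planned.

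**Working it through.** The SAP states no expected ERR, so there is no figure to reproduce. The point is algebraic; the ERR values used below are illustrations.

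**Inputs from the SAP**
- Response visits, fixed effects and formula: 10.2.4.
- ERR as a change between two visits: 9.2.
- Log transform: "A constant value of 1 will be added to all raw epg values to allow for the possibility of an epg value of 0" (9.2).
- Comparable baselines in expectation: "Randomisation will be 1:1:1 to each arm and stratified by school" (6.1).
- Only the baseline dose is scheduled in any arm before baseline + 4 weeks: 9.5.
- 100 participants per arm, used for the simulation: section 7.

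**Step 1: what βx is.** Write the model as

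E[log count, arm a, visit t] = b0 + b_a + g_t + d_at + c × baseline,

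with b, g and d equal to zero for control and for the reference visit. At the reference visit, arm a minus control is b_a. So βx = b_a is a between-arm log ratio at that visit, and control has no such coefficient.

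**Step 2: what each ERR needs.**
- From baseline, for a visit t: (b0 + b_a + g_t + d_at + c × mean log baseline) − mean log baseline. This is not b_a for any arm.
- From 24 months to 24 months + 4 weeks: the difference in g plus the difference in d for that arm. Here b_a cancels completely.

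**Step 3: what the formula returns for a baseline-referenced interval.** With equal baselines in expectation, exp(b_a) ≈ (1 − ERR_a)/(1 − ERR_control), so the formula gives 1 minus that ratio.

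| True ERR 1x / 2x / 4x | Formula, 2x | Formula, 4x |
|---|---|---|
| 90 / 90 / 90% | 1 − 0.10/0.10 = 0% | 0% |
| 90 / 90 / 95% | 0% | 1 − 0.05/0.10 = 50% |
| 90 / 85 / 80% | 1 − 0.15/0.10 = −50% | 1 − 0.20/0.10 = −100% |

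A single-visit regression simulated at 100 per arm agreed: −1% and 1%, −2% and 49%, −50% and −102%.

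**Step 4: the full model by simulation.** Assumptions: 300 replicates, 100 per arm, unstructured covariance, log baseline as covariate, log-normal baseline with median 300 epg and log-SD 1.2, visit noise with log-SD 0.8. Each visit was taken in turn as reference.
- True ERR 90% in every arm, equal 24-month levels, ln(epg+1): 1 − exp(βx) averaged −0.7% to +0.9% (SD about 11 to 16 points).
- True ERR 50% in every arm, ln(epg): −0.7% to +0.3%.
- Each arm clears 90% from 24 months to 24 months + 4 weeks, but 24-month levels are 0.8, 0.5 and 0.25 of baseline. By hand, 1 − 0.5/0.8 = 37.5% and 1 − 0.25/0.8 = 68.75%. Simulated with 24 months + 4 weeks as reference: 37.0% and 68.5%. The 90% does not appear.

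**Step 5: within-arm contrasts from the same model.** The contrasts were the adjusted arm mean minus mean log baseline for two intervals, and the arm-specific difference between the two 24-month visits for the third. For a true 90% they returned 89.9–90.0% with ln(epg) and 88.9–89.3% with ln(epg+1), across all three arms and intervals.

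**The case against.** The strongest defence is that 5.1.3 poses a between-arm question: how 2x and 4x compare with 1x on ERR. For the baseline-referenced intervals exp(βx) is close to the ratio of remaining egg fractions, which is a sensible answer to it. This stands in part. The coefficient is useful there, but it is not an ERR, and for the last interval the between-arm comparison lies in the interaction terms.

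Other codings do not rescue the sentence. If each arm had its own coefficient without an intercept, that coefficient would be a predicted log count at a baseline covariate of zero, not a change. If treatment effect were taken to mean the pre-to-post change, baseline would have to be in the response, or its slope fixed at 1; the model does neither.

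Three points on the other side stand in full.
- Descriptive ERRs are planned: the sample ERR in 9.2, the summaries by arm in section 10 (with a Standard of Care column under section 9), and the box plots in section 12.
- The specified model can supply the right contrasts, as step 5 shows.
- ERR is exploratory and does not enter the primary analysis, the gatekeeping sequence, the power calculation or the infection-intensity endpoint.

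**Conclusion.** The formula in 10.2.4 is wrong as written: it yields none of the nine ERRs that the section promises. For baseline-referenced intervals it returns about 1 − (1 − ERR_arm)/(1 − ERR_control), hence about 0% whenever the arms share the same ERR, whatever its level. The algebra rests only on the stated model and on randomisation; the 90% and 50% and the count distribution are assumptions for illustration.

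A reader might infer more than the document supports:
- *That the model-based value is near 0% whenever every arm clears 90%.* For 24 months to 24 months + 4 weeks this also needs equal 24-month levels; otherwise it is a different between-arm figure, such as 37% and 69% in the example.
- *That the report as a whole would make an effective drug look ineffective.* The descriptive ERRs per arm, including control, would still be shown correctly. The harm is two quantities under one name.
- *That the model must be rebuilt or a confirmatory conclusion is at risk.* Neither follows.

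**What to change.** 1. Delete the sentence that sets ERR equal to 1 − exp(βx).
2. Define each of the nine model-based ERRs as a within-arm contrast with a CI: 1 − exp(adjusted arm mean at the later visit − mean at the earlier visit). From the existing model, use the adjusted arm mean minus mean log baseline for the two baseline intervals, and the arm-specific 24 months + 4 weeks minus 24 months difference for the third. Making baseline a fourth response visit is equally acceptable.
3. If 1 − exp(treatment coefficient) is kept, report it only as a between-arm relative reduction and name the visit.
4. Label the model-based ERR as geometric-mean based. It comes from log counts, while 9.2 defines ERR on arithmetic means, so the two need not agree even after the correction.

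The cost is a few lines of SAP text and code. No new data are needed.

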9.5 Treatment Compliance

Information relating to the number of participants who missed the IMP at the required visit captured in the 'Non-Adherence to protocol' CRF as well as the 'IMP administration' CRF will be shown in a summary table and displayed as a stacked bar chart, each treatment group represented by their colour and position within the stack. The number missing will be a scale on the y axis and each treatment time—point will be ordered on the x axis.

- · Standard of Care Arm: Baseline, 12 months and 24 months
- Intervention Arm 1 (2 x treatment): Baseline, month 7, month 12, month 19 and month 24
- Intervention arm 2 (4 x treatment): Baseline, month 4, month 7, month 10, month 12, month 16, month 19, month 22 and month 24

Information relating to the number of participants who missed data collection visits captured in the 'Non-Adherence to protocol' CRF will be shown in a summary table and displayed using a stacked bar chart with each treatment arm represented by their colour and position within the stack, the number missing will be shown on the y axis and time-point on the x axis.

- Ultrasonography
- Parasitology
 - Standard of Care Arm: Baseline and 24 months
 - o Intervention Arm 1: Baseline and 24 months
 - o Intervention arm 2: Baseline and 24 months

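### SAP 10.2.4: the model-based egg reduction rate is a reduction relative to control at one visit, not the per-arm change between visits that the section promises

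*SAP*

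**What the plan says.** Section 9.2 defines the sample ERR from the ratio of a later to an earlier mean count: "Where epg1 and epg2 are the arithmetic mean of epg of faeces at" the two ends of each interval. The intervals are baseline to baseline + 4 weeks, baseline to 24 months + 4 weeks, and 24 months to 24 months + 4 weeks.

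Section 10.2.4 names the same three intervals. A repeated-measures mixed model with an unstructured covariance for the "within - patient residual errors will estimate the Egg Reduction Rate (ERR) between" those pairs of visits, and it is to do this "for each treatment group using log transformed epg counts at 3 time points (baseline +4 weeks, 24 months and 24 months + 4 weeks". The terms are then fixed: "The model will specify fixed effects of treatment, time and baseline epg count with an interaction term between treatment and time". Finally, the treatment coefficient βx "in this model quantifies the relative change and the ERR is given by" 1 − exp(βx).

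The dosing visits are in section 9.5:
- control: "Standard of Care Arm: Baseline, 12 months and 24 months"
- twice yearly: "Intervention Arm 1 (2 x treatment): Baseline, month 7, month 12, month 19 and month 24"
- four times yearly: "Intervention arm 2 (4 x treatment): Baseline, month 4, month 7, month 10, month 12, month 16, month 19, month 22 and month 24"

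Sections 5.1.3 and 5.2.2 class ERR as exploratory, although the heading of 10.2.4 calls it a secondary endpoint.

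**The concern.** An ERR answers how far counts fell in an arm between two visits. A treatment coefficient in a model adjusted for baseline answers how an intervention arm compares with control at one visit. Section 10.2.4 gives the second quantity the name of the first, and names neither a time contrast within an arm nor a comparison with the baseline mean.

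The risk is a report with two conflicting figures under one label: a descriptive ERR that reflects clearance after a dose, and a model ERR near zero for the same interval. A programmer following the text literally would also have no model figure for the control arm, though each arm is promised one.

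**Working it through.** The SAP states no numerical ERR, so there is no plan figure to reproduce. The check is algebra, then a simulation.

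**1. The model as written.** Let Y be ln(epg + 1) at visit t (B4 = baseline + 4 weeks, M24, M24+4), and B the baseline log count. For arm a:

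E[Y] = α + τ(a) + γ(t) + δ(a,t) + λB, with τ = δ = 0 for control and γ = δ = 0 at the reference visit B4.

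**2. What the coefficient is.** The treatment contrast at visit t is τ(a) + δ(a,t) = E[Y | a, t, B] − E[Y | control, t, B]. One minus its exponential is a relative reduction versus control. With B4 as reference visit, the main treatment coefficient τ(a) is that contrast at B4.

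**3. What an ERR needs.** On the log scale, within arm a:
- baseline to B4: α + τ(a) + λ·mean(B) − mean(B)
- M24 to M24+4: [γ(M24+4) + δ(a,M24+4)] − [γ(M24) + δ(a,M24)]
- baseline to M24+4: α + τ(a) + γ(M24+4) + δ(a,M24+4) + λ·mean(B) − mean(B)

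None of these is τ(a) or τ(a) + δ(a,t). A single arm contrast at M24+4 would have to serve for both intervals that end there.

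**4. Baseline to baseline + 4 weeks.** By section 9.5 every arm is dosed at baseline and none again before month 4. Under randomisation, expected log count at B4 given B is the same in all arms, so τ(a) = 0 and 1 − exp(0) = 0% for any clearance.

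**5. Simulation.** 200 trials per scenario, 100 per arm (the figure in SAP section 7), complete data, equal clearance per dose in all arms. Assumed, because the SAP gives no values: baseline log count mean 5.5, SD 1.2; person SD 0.5; residual SD 0.6; 24-month intensity relative to baseline 1, 0.6 and 0.3 for 1x, 2x and 4x. Fixed effects were estimated by ordinary least squares. Medians, in %:

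| Quantity | 50% clearance | 90% | 99% |
|---|---|---|---|
| 1 − exp(treatment coefficient) at B4, 2x | −0.4 | −1.1 | −1.7 |
| Same, 4x | −0.5 | −0.7 | −0.8 |
| Within-arm ERR, baseline to B4, 1x | 49.6 | 89.3 | 98.3 |
| Same, 2x | 48.6 | 89.1 | 98.3 |
| Same, 4x | 49.5 | 89.1 | 98.3 |
| 4x versus 1x contrast at M24+4 | 69.1 | 64.7 | 48.3 |
| Within-arm ERR, M24 to M24+4, 4x | 48.5 | 87.6 | 97.2 |
| Within-arm ERR, baseline to M24+4, 4x | 84.2 | 96.2 | 99.1 |

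At 90% clearance the 95% simulation range of the B4 coefficient figure was −27.9% to 18.3% (2x) and −25.5% to 19.3% (4x).

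At M24+4 with 90% clearance, the inputs before the +1 shift imply 1 − 0.3 = 70% versus control, 1 − 0.1 = 90% from 24 months, and 1 − 0.3 × 0.1 = 97% from baseline. The simulated 64.7%, 87.6% and 96.2% are these values pulled down by the +1. The between-arm figure matches neither ERR.

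One data set at 90% clearance was also fitted with a random-intercept mixed model. The treatment coefficients were −0.053 and 0.086, so 1 − exp gives about 5% and −9%: again near zero, not 90%.

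**6. Scale.** Even the right contrast in this model is on the geometric-mean scale, while 9.2 uses arithmetic means. As an assumed illustration, if 70% of children clear and 30% halve their counts, the arithmetic ERR is 1 − 0.3 × 0.5 = 85%. With a mean baseline log count near 5, the log version is 1 − exp(0.7 × (−5) + 0.3 × ln 0.5) = 1 − exp(−3.71), about 97.5%. This shows that the scales can differ, not by how much they will differ here.

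**The case against.** The best defence has three parts.

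First, a correct ERR is already planned. Section 9.2 defines it on arithmetic means for all three intervals, section 10 lists it for summary by arm at the follow-up visits, and section 12 plans plots of it by arm. This stands. A reader might infer that every ERR in the report will be wrong, or that control will have no ERR at all; the SAP does not support that, because the defect is confined to the model-based figure.

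Second, objective 5.1.3 is a comparison of arms. With baseline adjusted, the treatment contrast in log count equals the adjusted contrast in log change from baseline, so it answers that objective for the two intervals starting at baseline, and a value near zero at 4 weeks is then the right answer. This also stands, but only for a quantity labelled as a comparison with control. Section 10.2.4 says that it estimates ERR for each arm and interval.

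Third, the fitted model already contains the within-arm contrast from 24 months to 24 months + 4 weeks. True, but the section does not ask for it.

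Other readings do not rescue the text. Cell-means coding turns the coefficient into a log level, and a change score as outcome is not what is specified. A reader might also fear a false conclusion of drug failure. That is speculative, since the descriptive ERR and the cure rate from baseline to baseline + 4 weeks (10.2.6) would expose the discrepancy.

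**Conclusion.** The model-based ERR in 10.2.4 is wrong as written: it is a relative reduction versus control, it leaves control without a model ERR, and it uses one number for two intervals that end at the same visit. The expected log value of zero at baseline + 4 weeks follows from randomisation and identical scheduled dosing. It needs no assumption on clearance, but does need missed baseline doses (acknowledged in 16.1.2) to be balanced across arms. The simulated spread and the 24-month figures depend on the assumed inputs and are illustrations.

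This is a should-fix. ERR is exploratory, lies outside the gatekeeping sequence of section 8.6, and has no bearing on the primary conclusion.

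**What to change.** Rewrite the estimation paragraph of 10.2.4:

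- Include baseline as a fourth outcome visit, in place of the baseline covariate, and report 1 − exp(within-arm time contrast) with a 95% CI for each arm, control included, and each interval. Label it a geometric-mean ERR.
- Alternatively, make the arithmetic-mean ERR of 9.2 the reported ERR, per arm and interval, with a participant-level bootstrap 95% CI.
- Keep 1 − exp(treatment contrast), at a named visit, only for the between-arm objective, labelled as relative reduction versus control. For 24 months to 24 months + 4 weeks, the between-arm comparison of change is δ(a,M24+4) − δ(a,M24).
- Optionally add school, the randomisation stratum, as in 10.2.2, 10.2.3 and 10.2.5. This is a minor improvement.

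The cost is one paragraph of SAP text and a small programming change, with no new data.

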10.2.5 Analysis of secondary endpoint - Prevalence of infection

The burden of disease will be estimated by calculating the prevalence at 24 months. A binary variable indicating disease status will be created and each participant will be classed as either having Schistosomaisis or not using the average EPG at 24 months.

No Disease 0 = EPG = 0

Disease 1 = EPG > 0

A logistic regression model will be fitted to estimate the prevalence odds ratio adjusted for age, sex and school.

Note that an additional analysis was included post hoc which modelled prevalence of infection at 24 months adjusting for baseline $\ln(epg+1)$, age, sex and school.

10.2.6 Analysis of secondary endpoint - Cure rate

The cure rate as defined in section 9.2 will be calculated for the following time points:

- Baseline to 24 months
- Baseline to baseline +4 weeks
- 24 months to 24 months + 4 weeks

Cure rates will be presented by treatment arm and also stratified by baseline infection intensity; \geq 400 epg = Heavy infection / <400 - 1 epg = Medium - Light Infection.

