5.2.2 Exploratory endpoints

- Schistosoma mansoni Egg Reduction Rate (ERR) measured between:
 - Point Baseline and baseline +4 weeks
 - Baseline and 2 years + 4 weeks
 - o 2 years and 2 years +4 weeks
- Prevalence at 2 years post 1st treatment.
- Cure rate between:
 - Baseline and baseline +4 weeks
 - o Baseline and 24 months
 - Baseline and 24 months +4 weeks
- Adverse Events measured at baseline and 24 months:
 - Any AE (Yes/No)
 - Digestive AE's = 4,5,6,7,or 12 on CRF see Also section 11 of SAP (Yes / No)
 - Neurological AE's 1,2,3,8,9 or III on CRF see Also section 11 of SAP (Yes/No)

[figure not shown]
6 Study Methods

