The CR is the proportion of participants who have changed from an epg >0 to and epg of =0 between timepoints;

 $CR = \frac{Total\ number\ of\ participants\ who\ have\ an\ average\ epg\ =\ 0\ at\ timepoint\ 1}{Number\ of\ participants\ who\ have\ epg\ >\ 0\ at\ timepoint\ 0}$

Residency in Holma district is dichotomised into 2 years - 4 years/ > 4 years

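### Cure from 24 months to 24 months + 4 weeks is stratified by trial-baseline intensity, which does not align pre-dose intensity between arms; the cure intervals in SAP 5.2.2 and 10.2.6 also differ

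*SAP*

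**What the plan says.** SAP section 10.2.6 reports cure over three intervals: baseline to 24 months, "Baseline to baseline +4 weeks", and "24 months to 24 months + 4 weeks". It then applies a single rule to all of them: "Cure rates will be presented by treatment arm and also stratified by baseline infection intensity". After a ≥ sign, the strata read "400 epg = Heavy infection / <400 - 1 epg = Medium - Light Infection".

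Section 9.2 defines the quantity: "The CR is the proportion of participants who have changed from an epg >0 to and epg of =0 between timepoints". Its formula puts children with epg above 0 at the start of the interval in the denominator.

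Section 5.2.2 lists the cure-rate endpoints. Its first two intervals match section 10.2.6, but its third is "Baseline and 24 months +4 weeks".

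Section 9.5 gives the treatment visits. For the control arm it has "Standard of Care Arm: Baseline, 12 months and 24 months". The 2x arm is scheduled at baseline and months 7, 12, 19 and 24. For the 4x arm it has "Intervention arm 2 (4 x treatment): Baseline, month 4, month 7, month 10, month 12, month 16, month 19, month 22 and month 24".

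**The concern.** Section 10.2.6 uses baseline as the name of a visit, distinct from 24 months, and nothing in the SAP redefines it as the start of each interval. Read literally, the last interval takes its denominator from the 24-month visit and its strata from a count made about two years earlier. That count is older still at Buhirigi, where baseline data were collected in March 2020 (section 9.3) and the window before first treatment was later widened (section 15.1.1).

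Between the two counts the arms are scheduled for different numbers of doses, and section 5.1.2 makes the effect of dosing frequency on intensity a trial objective. Children in the same baseline stratum may therefore reach the month-24 dose with different intensities by arm. Higher cure in the 4x arm within a stratum could then be read as preserved or better drug response under frequent dosing, when it reflects lighter infection before the dose.

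The two lists of intervals raise a separate matter. Baseline to 24 months + 4 weeks spans the whole regimen, whereas 24 months to 24 months + 4 weeks spans a single dose.

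**Working it through.** The SAP states no cure rate and no figure on which this point depends, so there is nothing of its own to reproduce.

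**Step 1: doses between the stratifying count and the month-24 dose (section 9.5).**
- 1x: baseline and month 12, so 2. Last scheduled dose 24 − 12 = 12 months before.
- 2x: baseline and months 7, 12, 19, so 4. Last 24 − 19 = 5 months before.
- 4x: baseline and months 4, 7, 10, 12, 16, 19, 22, so 8. Last 24 − 22 = 2 months before.

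These are scheduled doses, not doses received.

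**Step 2: do the strata cover the denominator?** The denominator is epg > 0 at 24 months. The strata are ≥400 and 1 to <400 at baseline. A child with epg 0 at baseline and epg > 0 at 24 months is in the denominator and in neither stratum.

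**Step 3: size of the artefact by mixture arithmetic (assumed inputs).** Let h be the share of a baseline stratum, among children positive at 24 months, that is heavy at 24 months. Let cH and cL be cure in children heavy and light at 24 months, identical in every arm. Then:

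cure in stratum = h × cH + (1 − h) × cL

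4x minus 1x = (h in 1x − h in 4x) × (cL − cH)

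Assume h = 60%, 40%, 20% (1x, 2x, 4x) in the heavy-at-baseline stratum, with cL = 80% and cH = 50%:
- 1x: 0.6 × 50 + 0.4 × 80 = 62%
- 2x: 0.4 × 50 + 0.6 × 80 = 68%
- 4x: 0.2 × 50 + 0.8 × 80 = 74%

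The apparent gain is 12 points with no difference in drug response. With the same h, 4x minus 1x is 0.4 × (cL − cH): 0 points for 60/60, 8 for 70/50, 12 for 80/50 and 20 for 90/40. In the light-at-baseline stratum, with h = 25%, 15%, 5% and 80/50, cure is 72.5%, 75.5% and 78.5%, a gap of 6 points.

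**Step 4: simulation with one response curve for all arms (assumed inputs).** There were 400,000 children per arm. Log intensity at baseline had mean 5 and SD 1.8, with correlation 0.5 to 24 months. The 24-month mean was shifted by 0, −0.7 and −1.5 in the 1x, 2x and 4x arms. Log intensity of 1.5 or less counted as no eggs. Log odds of cure were 0.8 − slope × (ln(epg + 1) − 4.5). With slope 0.6, cure among children positive at 24 months was:

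| Group | 1x | 2x | 4x | 4x − 1x |
|---|---|---|---|---|
| Unstratified | 59.1% | 65.9% | 72.8% | 13.7 |
| Heavy at baseline | 47.1% | 55.5% | 64.6% | 17.5 |
| Light at baseline | 63.7% | 70.2% | 76.6% | 12.9 |
| Heavy at 24 months | 32.8% | 34.4% | 36.6% | 3.8 |
| Light at 24 months | 70.3% | 73.1% | 76.7% | 6.4 |

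The unstratified rate carries a similar gap, so the baseline strata fail to remove the imbalance; they do not create it. Stratifying at 24 months removes much of it. The remainder comes from the coarse 400 epg cut.

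**Step 5: when the artefact disappears.** With slope 0 (cure unrelated to intensity), cure is about 69% in every arm. With no effect of frequency on 24-month intensity and slope 0.6, the heavy-at-baseline rates are 47.2%, 47.0% and 47.2%.

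**The case against.** **The wording may be loose.** The strata omit zero, which exactly partitions children positive at the start of an interval, so the authors may have meant interval-start intensity. Section 10.3.1 also uses baseline loosely. This is possible, but section 10.2.6 names baseline as a visit and section 10.2.4 uses baseline epg in the same sense. The literal reading is the more natural one.

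**A baseline covariate respects randomisation.** That does not help here: the denominator is fixed by positivity at 24 months, so it is already a post-randomisation subgroup under either stratifier.

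**Other outputs limit misreading.** Intensity and heavy infection at 24 months are summarised and modelled by arm (sections 10, 10.2.2, 10.2.3) and shown in alluvial plots (10.2.7). Egg reduction over the same four weeks is estimated (10.2.4). This stands: a careful reader could see the imbalance, although the cure table would not adjust for it.

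**Stronger readings that the SAP does not support.** A reader might infer that the 4x arm is bound to show higher cure. It is not: both conditions must hold, the first among children still positive, and whether frequency lowers intensity is what the trial is testing. If children still positive under frequent dosing are harder to cure, the gap can be offset; one simulated case gave 46.9%, 47.4% and 45.6% in the heavy-at-baseline stratum, though that is no longer equal response.

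A reader might also take a gap between two individual children as the bias between arms. Assume six slides (the maximum in section 6.4) of 1/24 g and Poisson counts. After a 95% reduction, a child at 400 epg tests negative with probability exp(−0.25 × 20) = 0.7%, and one at 100 epg with exp(−0.25 × 5) = 29%. This shows why apparent cure can fall with pre-dose intensity. It does not measure a difference between arms, which depends on how far the arms' intensities separate.

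**Conclusion.** The point holds in conditional form. For the interval starting at 24 months, the baseline stratifier does not align pre-dose intensity between arms and leaves some of the denominator unclassified. Both follow from the text without assumptions. So does the conflict over the third interval.

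The bias needs two conditions for which the SAP gives no figures: lower 24-month intensity in the more-treated arms among children still positive, and lower cure at higher pre-dose intensity. On the assumed inputs the artefact in the heavy stratum runs from 0 to about 20 points between 4x and 1x.

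The consequence is limited. Cure rate is exploratory in sections 5.1.3 and 5.2.2, although 10.2.6 is headed as a secondary endpoint, and the rates are only presented, without a model or test. The two intervals that start at baseline are stratified consistently. If the lists are reconciled so that the 24-month interval is dropped, the stratification problem goes with it.

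**What to change.** 1. In section 10.2.6, stratify each cure rate by epg at the start visit of its own interval: baseline epg for the intervals that start at baseline, 24-month epg for 24 months to 24 months + 4 weeks. Every child in the denominator then falls in a stratum.
2. State that the last interval compares subgroups formed after randomisation. It describes drug response and is not a randomised effect of treatment frequency. This applies to the unstratified rate as well.
3. Note that a single cut at 400 epg leaves some imbalance within strata, and that the heavy stratum at 24 months may be small in the 4x arm.
4. Make the interval lists in sections 5.2.2 and 10.2.6 the same.

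The cost is SAP wording and one changed table. The 24-month egg count is already collected (section 6.4), so no new data are needed.
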